Official Title: An Open Label, Proof-of-Principle, Pilot Study to Evaluate Pimavanserin
for the Treatment of Motor and Behavioral Symptoms of Tourette Syndrome.

NCT Number: Pending

Document date: 23FEB2021

Data at baseline and scheduled follow up visits per study protocol will be collected in the form of standardized rating scales used to measure symptom severity in Tourette syndrome as described below.

The primary endpoint is the change in the Total Tic Score (TTS) of the Yale Global Tic Severity Scale (YGTSS) from baseline to week 8 in TS patients treated with pimavanserin. The goal is to see if pimavanserin has an effect on this score. A reduction in score would indicate a clinical benefit and vice versa.

If this score is reduced from baseline to week 8 while taking the study drug, this will suggest clinical benefit. Any degree of reduction in this score will be described as a suggestion of clinical benefit. A similar approach will be applied to the other scales mentioned in the study protocol. If there is suggestion of clinical benefit, we will consider this an indication of feasibility for a larger study.

Secondary endpoints include changes from baseline to week 8 in: - Yale-Brown Obsessive Compulsive Scale (Y-BOCS) - Tourette Syndrome-Clinical Global Impression (TS-CGI) score - Tourette Syndrome-Patient Global Impression of Impact (TS-PGII) score - Gilles de la Tourette syndrome-quality of life scale (GTS-QOL) - Global Severity Score (GSS) of the YGTSS - Motor Tic Severity Score (MTSS) of the YGTSS - Vocal Tic Severity Score (VTSS) of the YGTSS - YGTSS Impairment score - Proportion of patients who have a reduction of 6 or more points in the TTS of the YGTSS - Proportion of patients who have a TS-CGI reduction of 2 or more points - Observed values and change in patient-assessed Tic-free Interval assessment.

All these variables will be analyzed over the 8 week treatment period. The data will be analyzed using standardized software and statistical tools as indicated. The data will be presented in the form of graphs/tables showing the change in scores over the 8 week treatment period.

Safety Analyses: All adverse events will be coded using the Medical Dictionary for Regulatory Activities. Summaries will be presented for all adverse events, adverse events determined by the investigator to be related to study treatment, serious adverse events, and adverse events causing withdrawal from the study. Patient listings of serious adverse events and adverse events leading to withdrawal will be presented. Observed values and changes from baseline in laboratory results, vital signs and EKG parameters will be summarized descriptively. The use of concomitant medications will be monitored and will include all medications taken while the patient is treated with IMP.

Observed values in the C-SSRS will be monitored for all patients.

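### Do the endpoint and the benefit rule in the SAP use different patients once someone stops pimavanserin before week 8?

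*SAP*

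**What the plan says.** The SAP's second paragraph sets the primary endpoint: the change in the TTS of the Yale Global Tic Severity Scale "from baseline to week 8 in TS patients treated with pimavanserin". The third paragraph gives the rule for reading it: "If this score is reduced from baseline to week 8 while taking the study drug, this will suggest clinical benefit". It adds that "Any degree of reduction in this score will be described as a suggestion of clinical benefit", and that "If there is suggestion of clinical benefit, we will consider this an indication of feasibility for a larger study".

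Among the secondary endpoints are two responder proportions, one of them "Proportion of patients who have a reduction of 6 or more points in the TTS of the YGTSS". The closing efficacy paragraph says "All these variables will be analyzed over the 8 week treatment period". The opening paragraph leaves the visit schedule to the protocol: "Data at baseline and scheduled follow up visits per study protocol will be collected". The Safety Analyses section foresees early leavers, since it summarises "adverse events causing withdrawal from the study".

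The SAP names no efficacy analysis set. It does not say whether a week-8 score taken off drug, or the last score of a patient who stopped early, is used.

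**The concern.** Read quickly, the endpoint covers everyone who received the drug, while the rule counts only those still on it at week 8. If so, the SAP would define one quantity and draw its conclusion from another.

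The benefit rule raises the stakes, because any reduction counts and so the sign of the mean change decides the call. If patients leave because their tics worsen, a mean over those who remain tilts towards benefit, and that call then feeds the statement on feasibility of a larger study. The responder proportions raise a similar question about the denominator.

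**Working it through.** The SAP gives no sample size, standard deviation or dropout rate, so there is no figure of its own to reproduce. The check is a reading of the text, followed by illustrations on assumed values.

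**Reading the sentences together.** The endpoint refers to patients treated with the drug. It does not say all of them, and it does not exclude those who stop. The rule refers to a reduction over the same interval while on drug. The study is open label with one treatment, and the variables are analysed over the 8-week treatment period. In that setting the on-drug clause can simply restate the period, and the two sentences then agree.

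**When the two readings could differ.** They differ for the mean only if an early stopper has a score that one reading counts and the other leaves out. A stopper with no week-8 score enters neither mean unless a value is imputed, and the SAP proposes no imputation. Whether patients are seen after stopping is a protocol matter, and the protocol was not available for this check.

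**Size for the mean.** Let d be the share who stop early, m_on the mean change on drug and m_stop the mean change among stoppers. Then

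mean over all treated = (1 - d) × m_on + d × m_stop,

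which reaches zero at m_stop = -(1 - d) × m_on / d. For d = 20% and m_on = -1 this is 0.8 × 1 / 0.2 = +4.0 points. Over a range of assumed values:

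| On-drug mean change | d = 10% | d = 20% | d = 30% |
|---|---|---|---|
| -1 | +9.0 | +4.0 | +2.3 |
| -3 | +27 | +12 | +7 |
| -6 | +54 | +24 | +14 |

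If stoppers average no change, the overall mean is (1 - d) × m_on. The sign never reverses and only the size shrinks; for example, -1 becomes -0.8 at d = 20%.

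**Chance of a benefit call.** This is a simulation with normal changes and 20% dropout; sample size, dropout rate and dependence on worsening are all assumed. With a true change of zero, the chance that the on-drug mean shows a reduction, for 10 / 20 treated, is:

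- random dropout: 50% / 50%
- dropout odds doubling per SD of worsening: 65% / 70%
- dropout odds multiplied by 2.7 per SD: 70% / 77%
- exactly the worst 20% leave: 83% / 93%

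The 50% under random dropout comes from the any-reduction rule, not from who is counted. With a true change of -0.5 SD and odds doubling per SD, the on-drug mean shows a reduction in 96.4% of trials against 94.2% for all treated at 10 patients, and 99.5% against 98.7% at 20. The gap falls from about 15 to 20 percentage points to 1 or 2.

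**Responder proportions.** With 10 treated, 2 stopping and 3 responders, 3/8 = 37.5% and 3/10 = 30%. The denominator matters, but a proportion of patients reads naturally as a proportion of all patients in the study.

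**Would a prescribed estimator help?** The setting is two visits correlated 0.7, 10 patients and no true change, so an unbiased method would show a reduction 50% of the time. The ranges cover the two graded dropout strengths above.

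| Dropout driven by | Completers | Repeated-measures model | Last on-treatment score |
|---|---|---|---|
| Observed earlier score | 60.1% to 63.8% | 50.5% to 50.8% | 46.3% to 45.0% |
| Unseen week-8 score | 64.6% to 69.7% | 58.3% to 61.4% | 53.9% to 55.4% |

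The model does better in the first case and the last score in the second. Which one to prefer depends on a dropout mechanism nobody knows in advance, and both still use on-treatment scores only.

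**The case for a change.** The strongest contrary argument is that analysis sets and the handling of early stoppers are core SAP content, so the protocol cannot be relied on to settle them. The SAP expects withdrawals yet deals with them only under safety. Because sign alone decides, a modest selection effect could settle the call: with no true change and worsening-related dropout at the two graded strengths, the on-drug mean showed a reduction while the mean over all treated did not in 16% and 21% of simulated trials at 10 patients, and in 21% and 27% at 20. One sentence would close the gap at almost no cost.

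Part of this stands. The SAP is silent on early stoppers, and a clarifying sentence would do no harm. The percentages carry less weight. They assume no true effect and dropout driven by worsening tics, and they compare against week-8 scores from stoppers that the trial may never collect. The only withdrawals the SAP mentions are those caused by adverse events, and intolerance unrelated to tics does not bias the mean. Reporting completers beside the feasibility statement would add content, not correct an error.

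**Conclusion.** The claimed conflict is not in the text. The endpoint and the benefit rule can be read as the same analysis, and they give identical results if everyone completes 8 weeks. What is left is an unstated detail of the kind an analyst of a small open-label pilot fills sensibly: show the scores by visit, say how many patients contribute, and give responders out of all patients.

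No rule written in the SAP has been shown to give a wrong answer. The call would reverse only if the on-drug change were small and stoppers clearly worsened, for instance -1 point on drug with stoppers worse by more than 4 points at 20% stopping. With a change of -6 points, stoppers would have to worsen by more than 24. All of this rests on assumed sample size, dropout and dependence on worsening. The more elaborate remedies swap one debatable estimator for another. The weakness of a rule that accepts any reduction is a separate matter, and defining the analysis set would not cure it. No change to the plan is called for on this point.

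### Any fall in TTS is to be called a suggestion of benefit: the threshold is zero, no measure of uncertainty is attached, and the only contrast is uncontrolled

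*SAP*

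**What the plan says.** The SAP is unnumbered; the relevant text is its efficacy part. The title describes an open-label, proof-of-principle pilot, and the primary endpoint is the change in YGTSS Total Tic Score (TTS) from baseline to week 8 in treated patients.

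- **Aim:** "The goal is to see if pimavanserin has an effect on this score".
- **Reading rule:** "If this score is reduced from baseline to week 8 while taking the study drug, this will suggest clinical benefit", followed by "Any degree of reduction in this score will be described as a suggestion of clinical benefit".
- **Extension:** "A similar approach will be applied to the other scales mentioned in the study protocol".
- **Consequence:** "If there is suggestion of clinical benefit, we will consider this an indication of feasibility for a larger study".
- **Minimum changes used elsewhere:** the secondary endpoints include "Proportion of patients who have a reduction of 6 or more points in the TTS of the YGTSS" and "Proportion of patients who have a TS-CGI reduction of 2 or more points".
- **Presentation:** "The data will be presented in the form of graphs/tables showing the change in scores over the 8 week treatment period".

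Just before the presentation sentence, a general statement leaves the choice of software and statistical tools open. It names no method and is not linked to the reading rule. A further sentence says that a reduction would indicate benefit and the converse; it is taken here only as giving the direction of the scale.

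**The concern.** The SAP commits in advance to a description of the result that depends on nothing but its sign. Falls of 0.1 and 10 points would get the same words, and so would a precise and an imprecise estimate. A rule of this kind can hardly tell a promising result from noise, yet it is the stated route to the feasibility statement.

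The second problem is independent of the first. The aim is worded as a drug effect, but the data can show only a change over time in people who know they are being treated. Expectation, or any other non-drug change, produces the same pattern. A tighter estimate does not help with this.

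At stake are the wording of the report and the basis on which a larger study is called feasible. No efficacy claim is at stake.

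**Working it through.** **Inputs.** From the SAP: the threshold (change below zero), the contrast (baseline to week 8, treated patients, no comparator named) and the responder cut-off of 6 TTS points. The SAP gives no sample size or SD, so there is no planned figure to reproduce. Assumed for illustration: SD of the TTS change 6 to 8 points, n = 10 to 20, normal changes, and whole-point scores where stated. The SAP does not say whether the rule applies to the group mean or to each patient, so both readings are shown.

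**1. Group mean, no true change.** For a continuous, symmetric change, P(mean < 0) = Φ(0) = 0.50 for any n and any SD. This needs no assumed n or SD.

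With whole-point changes the mean is sometimes exactly zero, and by symmetry P(mean < 0) = (1 − P(mean = 0)) / 2:

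| SD | n | P(mean = 0) | P(mean < 0) |
|---|---|---|---|
| 6 | 10 | 0.021 | 0.489 |
| 6 | 20 | 0.015 | 0.493 |
| 8 | 10 | 0.016 | 0.492 |
| 8 | 20 | 0.011 | 0.494 |

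The answer is therefore about 49% instead of 50%, which makes no practical difference.

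**2. Precision of the mean.** 95% half-width = t(0.975, n−1) × SD / √n:

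- n = 10: 2.262 × 6 / √10 = 4.29 and 2.262 × 8 / √10 = 5.72 points.
- n = 20: 2.093 × 6 / √20 = 2.81 and 2.093 × 8 / √20 = 3.74 points.

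Under these assumptions a mean fall of 1 or 2 points satisfies the rule while its interval includes zero.

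**3. Patient by patient, no true change, whole points.**

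- Any fall (1 point or more): Φ(−0.5/SD) = 0.467 (SD 6), 0.475 (SD 8).
- Fall of 6 or more: Φ(−5.5/SD) = 0.180 (SD 6), 0.246 (SD 8).

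On this reading nearly half of unchanged patients would show a suggestion of benefit, against 18% to 25% at the SAP's own responder cut-off.

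**4. Attribution.** If the group mean falls by d points for reasons other than the drug, P(mean < 0) = Φ(d√n / SD). This exceeds 0.50 for every d > 0 and rises with n. As a pure illustration, d = 2 gives 0.79 to 0.85 at n = 10 and 0.87 to 0.93 at n = 20 (SD 8 to 6). The SAP gives no basis for choosing d, so only the direction is relied on: with such drift, more patients make a misleading reading more likely.

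**The case against.** The strongest reply is that this is a declared open-label pilot. Lack of attribution is inherent in that design, and the text speaks only of a suggestion and of feasibility. This stands as far as it goes: a control arm, power or a formal test should not be demanded, and the absence of a comparator is inferred from the SAP because the protocol was not examined. It does not excuse an aim worded as a drug effect, or a rule that the stated contrast cannot support.

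It can also be said that tables of change scores may well carry SDs or intervals, and that the open wording on statistical tools leaves room for them. That is fair. The claim is therefore limited to the reading rule, which is met by sign alone whatever else is tabulated.

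The responder cut-offs apply to patients, whereas the rule most naturally applies to the group. They are not a contradiction, only a sign that the authors recognise minimum changes elsewhere.

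Finally, removing the rule leaves no stated criterion for proceeding to a larger study. This is true, and it leaves more to judgement. But a criterion met half the time when nothing changes gives little guidance, and estimates with intervals are what the designers of the next study need.

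**Conclusion.** The concern holds. It is a fault in a stated rule, not a missing detail, and it should be corrected. On the group-mean reading the rule is met with probability 0.50 under no true change; that figure rests only on a symmetric, continuous change. The 49%, the patient-level percentages and the interval widths depend on assumed n, SD, normality and whole-point scoring, and they illustrate the point without describing this trial. No size is claimed for the attribution fault. The importance is moderate: hedged wording and a pilot setting limit the harm to how the result is described and to the argument for a larger study.

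**What to change.** 1. Keep the sentence on the meaning of a reduction solely as scale direction, for example: *On the TTS, lower is better.*
2. Reword the aim ("The goal is to see if pimavanserin has an effect on this score") as: *to estimate the within-patient change in TTS over 8 weeks of open-label pimavanserin.*
3. Replace the four sentences that state the reading rule, its extension to the other scales and its link to feasibility with: *For TTS and each other scale, the mean change from baseline (or the proportion, for responder endpoints) will be reported with its 95% confidence interval; without a control group it cannot be attributed to the drug and will be used only to inform the decision on, and design of, a controlled study.*

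The interval deals with the zero threshold and the missing uncertainty. The attribution clause deals with the uncontrolled contrast, which the interval alone would not.

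The cost is a change of wording in the SAP and report and one interval per scale or proportion. No new data and no design change are needed. The price is a more modest claim.

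### Does extending the 'reduction suggests benefit' reading to the other scales reverse the Tic-free Interval or leave the two responder proportions undefined?

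*SAP*

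**What the plan says.** The SAP has no numbered sections; all the relevant text is in the paragraphs on the primary and secondary endpoints.

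- For the primary endpoint, the change in YGTSS Total Tic Score from baseline to week 8, it states: "A reduction in score would indicate a clinical benefit and vice versa".
- The threshold is any fall at all: "Any degree of reduction in this score will be described as a suggestion of clinical benefit".
- The reading is then extended: "A similar approach will be applied to the other scales mentioned in the study protocol". A suggestion of benefit is in turn taken as a sign that a larger study is feasible.
- The opening paragraph describes the data as "standardized rating scales used to measure symptom severity in Tourette syndrome as described below".
- The secondary list begins "Secondary endpoints include changes from baseline to week 8 in" and has 11 items. Three matter here. The first is the tic-score responder endpoint: "Proportion of patients who have a reduction of 6 or more points in the TTS of the YGTSS". The second is its counterpart on the clinician's global rating: "Proportion of patients who have a TS-CGI reduction of 2 or more points". The third is the last item in the list: "Observed values and change in patient-assessed Tic-free Interval assessment".

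The SAP states a favourable direction for the TTS only. It does not say how the Tic-free Interval is scored.

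**The concern.** The only direction of benefit in the SAP is downward, and the extension names no exception.

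A tic-free interval, going by its name, is time without tics, so a longer one is better. Under a literal rule, a shortening interval would be reported as suggested benefit and a lengthening one as the opposite.

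The responder proportions raise a different difficulty. They sit under a heading about change from baseline, yet each is itself defined by change from baseline. No patient can be a responder at baseline, so the proportion cannot fall and a reduction rule could never show benefit.

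If both readings held, 3 of 11 secondary endpoints (3/11 = 27%) would be misread or could not be evaluated. One of them is a patient-assessed tic measure. Because a suggestion of benefit feeds the judgement about a larger study, a wrong sign could matter beyond presentation.

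**Working it through.** The SAP gives no sample size, alpha or power that bears on this point, so there is no figure to reproduce. The check is to apply the literal rule (change below 0 is benefit, change above 0 is the reverse) to each listed endpoint, and then to ask whether the text requires that rule.

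**Eight scale scores** (Y-BOCS, TS-CGI, TS-PGII, GTS-QOL, and the YGTSS Global Severity, Motor, Vocal and Impairment scores). The SAP presents its scales as measures of severity and gives no sign that any of these runs the other way. No conflict is shown.

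**Tic-free Interval** (one endpoint).
- If recorded as a duration, longer is better and the literal rule has the wrong sign.
- If recorded in categories ordered from long to short intervals, a lower value is better and there is no conflict.
- The SAP does not say which applies. Instrument scoring is ordinarily given in the protocol, to which the extending sentence refers.

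**Responder proportions** (two endpoints).
- A patient's reduction at baseline is 0, which is below both 6 and 2. The baseline proportion is therefore 0 by construction, or undefined.
- The week-8 proportion lies between 0 and 1, so week 8 minus baseline is never below 0. Taken literally, the rule could never signal benefit.
- Reaching that result means applying the rule twice: once inside the definition, where a responder is a patient whose score falls, and again to the count of such patients. The SAP does not call for the second step.

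**Does the text require the literal rule?** Two features say not.
- The extension is of a *similar* approach to the other *scales*. The natural reading is that any change in the favourable direction, however small, suggests benefit. A proportion of patients meeting a threshold is not a rating scale.
- The list heading cannot be read strictly for every item. Joined to its last item, it would give changes in observed values and in change, which is not a quantity anyone would compute. It is a loose heading, and the proportions have one plain meaning: the share of patients whose change from baseline to week 8 reaches the threshold.

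On that reading, none of the 11 endpoints is reversed or undefined.

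**The case for a change.** The best argument for a change is that a SAP should fix interpretation before data are seen, all the more so in an open-label study where the reading could be chosen afterwards. The only direction on the page is wrong for a duration, the heading is faulty for the responder endpoints however the Tic-free Interval is scored, and correcting both would need only a few words.

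Part of this stands. The SAP does not state which direction is favourable for the Tic-free Interval, and its heading does not suit a proportion already defined by change.

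The risk of a reading chosen after the fact does not stand. Once the scoring of the interval is known, its favourable direction follows from what it measures and leaves no real choice. The responder definitions fix their own direction and thresholds. The SAP also plans to report observed values as well as change for the interval and to show results in graphs and tables, so a sign error would be visible to any reader.

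An exact confidence interval and an all-treated denominator for the proportions might also be proposed. Neither bears on direction, so neither would answer this concern.

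**Conclusion.** The concern does not call for a change. It correctly notes that the SAP states no direction for one endpoint (1 of 11) and that the list heading fits two others loosely (2 of 11). It does not show that any conclusion would be reversed or undefined. The reversal needs a duration scoring that the SAP does not state, together with an analyst who treats less tic-free time as improvement. The responder problem needs a baseline responder rate that no analyst would calculate.

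This rests on two assumptions: that the scoring of the Tic-free Interval is available to the analyst outside the SAP, and that a similar approach means a change in the favourable direction. Both are ordinary readings. The primary TTS reading is untouched, the analysis is descriptive, and spelling out the directions would produce the same tables and the same conclusions.

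### The feasibility statement rests on the sign of the change alone and names no endpoint, so even on its natural TTS reading an inert drug would meet it about half the time

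*SAP*

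**What the plan says.** The SAP is unnumbered; the relevant text is the primary endpoint paragraph and the one after it.

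- The primary endpoint is the TTS change from baseline to week 8, with the aim "The goal is to see if pimavanserin has an effect on this score" and the reading "A reduction in score would indicate a clinical benefit and vice versa".
- The next paragraph opens: "If this score is reduced from baseline to week 8 while taking the study drug, this will suggest clinical benefit".
- It sets the size needed: "Any degree of reduction in this score will be described as a suggestion of clinical benefit".
- It extends the rule: "A similar approach will be applied to the other scales mentioned in the study protocol".
- It draws the conclusion: "If there is suggestion of clinical benefit, we will consider this an indication of feasibility for a larger study".

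A size does appear in the secondary endpoint list: "Proportion of patients who have a reduction of 6 or more points in the TTS of the YGTSS". That is a per-patient threshold, and nothing links it to the feasibility sentence. The same list contains eight secondary scale scores: Y-BOCS, TS-CGI, TS-PGII, GTS-QOL, GSS, MTSS, VTSS and YGTSS Impairment. The title describes the study drug as being evaluated "for the Treatment of Motor and Behavioral Symptoms of Tourette Syndrome".

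**The concern.** There are two weaknesses, of unequal weight.

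The first holds on every reading. The label depends on the direction of the change and on nothing else. A fall of a fraction of a point, with an interval reaching well into worsening, earns the same description as a large and precise fall. The label is then the basis for calling a larger study feasible.

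The second is an ambiguity. The feasibility sentence uses the label without saying which scale must earn it, and it comes directly after the sentence that extends the approach to the other scales. No rule covers the case in which TTS does not fall but another score does. If the reading is not settled beforehand, it can be settled after the results are known.

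At stake is how this pilot's result is described and how far it can support a larger study. No efficacy claim or formal test depends on it.

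**Working it through.** The SAP gives no sample size, SD, correlation or error rate, so there is no stated figure to reproduce. It also does not say how a reduced score is summarised; a group mean is assumed below.

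**1. Which endpoint does the text point to?** The phrase about suggesting benefit is introduced for TTS, which is the primary endpoint and the stated goal. That favours a TTS reading. The extension to other scales then comes between the definition and the feasibility sentence, and no scale is named. TTS is the natural reading, but a secondary-scale reading is not excluded.

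**2. Sign rule on TTS.** Let the mean change be normal with true value δ and standard error SE. Then P(fall) = Φ(−δ/SE). For an inert drug with no drift, δ = 0 and P = Φ(0) = 0.50. This does not depend on n or SD.

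Now suppose improvement unrelated to the drug. Take TTS as MTSS + VTSS (assumed), each with equal SE, correlation ρ and a downward drift of 0.5 SE. The sum shifts by 1 and has SD √(2 + 2ρ), so P(fall) = Φ(1/√(2 + 2ρ)).

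- ρ = 0.5: Φ(1/1.732) = Φ(0.577) = 0.718.
- ρ from 0.9 to 0: 0.696 to 0.760.

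**3. What the sign leaves out.** The 95% half-width is t(0.975, n − 1) × SD/√n. With assumed n of 10 or 30 and assumed SD of TTS change of 5 or 10 points:

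| n | SD 5 | SD 10 |
|---|---|---|
| 10 | 3.58 | 7.15 |
| 30 | 1.87 | 3.73 |

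An observed mean fall of 1 point meets the present wording. Its upper limit would be a rise of 1.87 − 1 = 0.87 up to 7.15 − 1 = 6.15 points.

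**4. One illustration of the any-scale reading.** Assumptions:

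- lower is better on every scale;
- TTS = MTSS + VTSS and GSS = TTS + Impairment, which leaves seven non-derived scores (Y-BOCS, TS-CGI, TS-PGII, GTS-QOL, MTSS, VTSS, Impairment);
- normal mean changes with a common correlation ρ, an inert drug and no drift.

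For m scores, P(at least one falls) = 1 − ∫φ(t)Φ(t√(ρ/(1 − ρ)))^m dt. At ρ = 0.5 the integral is 1/(m + 1), so for m = 7 the result is 1 − 1/8 = 0.875. Over ρ from 0.9 to 0 it runs from 0.670 to 0.992.

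A fall in TTS implies a fall in MTSS or VTSS. So P(TTS does not fall but another score does) = 0.875 − 0.5 = 0.375 at ρ = 0.5, with a range of 0.170 to 0.492.

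Treating TTS and all eight listed scores as nine separate scores instead gives 1 − 1/10 = 0.900, and 0.900 − 0.5 = 0.400. The structure assumed matters little; the correlation matters more. Mean changes of exactly zero are ignored and would lower all the sign figures slightly.

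**The case against.** The best defence is that this is descriptive language in an open-label, proof-of-principle pilot. The verbs are soft, and no hypothesis, error rate or efficacy claim is attached. The label is introduced for TTS only, and nothing says that one secondary scale is enough. Size is not missing from the plan either: score changes will be tabulated and graphed, and two responder proportions are listed. The any-scale figures rest on a correlation and a scale structure that the SAP does not give.

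Most of this stands, and it limits the point. A reader might infer that the SAP makes a fall on any single scale sufficient, or that the sponsor means to choose the reading after seeing the results. The text supports neither; it only fails to exclude them. A reader might also take 50% or 87.5% as a type I error rate. No test is planned, so these figures show only how little the label discriminates. Nor does the SAP state that there is no control group. It describes an open-label study measuring change in treated patients and mentions no comparator, and the protocol was not available for this review.

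The defence does not answer the express wording. The SAP itself says that any degree of reduction earns the label and makes the label the basis for feasibility. That is a rule fixed badly, not a detail left to the protocol. The sizes tabulated elsewhere play no part in it.

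**Conclusion.** The point holds in a limited form. On the natural TTS reading the feasibility statement depends on sign alone, and an inert drug with no drift would meet it about 50% of the time. This figure needs only a symmetric distribution of the mean change. Under the drift assumed above it is roughly 70% to 76%.

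The missing endpoint name is the lesser fault. It leaves open a favourable statement when TTS has not improved. The 87.5% figure for at least one of seven scores falling is an illustration at an assumed correlation of 0.5, and the conclusion does not depend on it.

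The wording should be settled before the data are seen. Nothing here calls for a hypothesis test, a power calculation or an interval lying wholly below zero.

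**What to change.** Replace the sentence beginning with any degree of reduction, and the feasibility sentence, with text such as:

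> The mean TTS change at week 8 will be reported with its 95% confidence interval, beside the planned 6-point responder proportion. A fall will not be labelled as suggesting benefit on its sign alone. The feasibility statement will rest on this TTS result, together with any behavioural scale the sponsor names before the data are seen. The remaining scales are supportive, and discordant results will be reported as such.

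Bring the two earlier sentences that equate a reduction with benefit into line: a lower TTS is the favourable direction, not in itself evidence of benefit. The sentence on a similar approach for the other scales should then refer to this way of reporting and not to the old label. If a behavioural scale is named, the SAP should also say whether it can carry the feasibility statement without TTS.

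The cost is SAP wording only, with two downsides. A favourable result on an unnamed secondary scale alone could no longer support the statement. That is a real loss given that the title covers behavioural symptoms, and it is why naming a scale is left to the sponsor. Reading by size and precision also leaves some judgement that a sign rule does not; a sponsor who wants less can state in advance what size of change would count.
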